In animals, WS extracts have also been shown to be safe in toxicity studies. Acute and sub-acute toxicity of a hydroalcoholic root extract of WS was investigated in female Wistar rats.⁴⁴ No behavioral signs of toxicity or gross pathological changes were observed with acute doses up to 2000 mg/kg. Similarly, no signs of subacute toxicity were observed in rats given 500, 1000 or 2000 mg/kg of the extract daily for 28 days. In a separate study, a hydroalcoholic root extract of WS was used to assess prenatal developmental toxicity in rats at doses of 500, 1000 and 2000 mg/kg daily for 28 days.⁴⁵ No signs of toxicity, gross pathology changes, or mortality were observed in the pregnant rats or fetuses. Further studies are required to examine the safety of WS extracts prepared using other extraction methods and plant parts.

In humans, the widespread use of WS as a traditional medicine and dietary supplement, as well as current scientific literature, support its general safety. In a review of clinical trials that used root preparations of WS for a wide variety of conditions, the authors noted that reasonable safety outcomes were seen with no serious adverse events or changes in vital signs or hematological and biochemical parameters.⁴⁶ Mild to moderate transient adverse events including somnolence, giddiness, vertigo, drowsiness, and gastrointestinal effects (e.g., nausea, epigastric pain, loose stools, constipation, decreased appetite) were reported in some studies, while other studies involving adults and children did not report any adverse events.⁴⁶ Similarly, an earlier review reported that WS has been used in all age groups and in both sexes, even during pregnancy, without any reported side effects.¹⁰ One study formally measured the tolerability of a WS root extract using the Patient's Global Assessment of Tolerability to Therapy and found it to have a high tolerability score.⁴⁷ Rare, serious adverse events have been reported, however. Isolated cases of mild to severe liver toxicity have occurred, with three deaths in patients who had underlying liver disease.⁴⁸⁻⁵⁰ A case report has also been published detailing a kidney transplant rejection due to WS.⁵¹ Liver and renal abnormalities will be assessed at the beginning and end of each four-week study period.

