Tolerability and safety: Participants' weight, height, body mass index, age, blood pressure, temperature, respiration rate, and pulse rate will be recorded at each study visit to monitor for adverse events and asymptomatic illnesses that may impact study results. Vitals will be collected at baseline, 7 hours post-Shoden administration, and at the end of each baseline visit. At the beginning of each baseline visit, participants will complete an electrocardiogram (ECG) and the Geriatric Depression Scale-15. Four teaspoons of blood (20 ml) will be collected for safety labs (CBC, CMP, urinalysis, TSH, serum total testosterone). ECG will be repeated 7 hours post-intervention to assess for cardiac changes. One teaspoon (5 ml) will be collected for a repeat CMP at 10 hours post-intervention to evaluate kidney and liver function. Participants will be interviewed and administered a standardized multi-system adverse events questionnaire at the beginning and end of each baseline visit. This visit is expected to take 13 hours a total of 175 mL of blood will be collected.

If the baseline CBC shows hemoglobin or hematocrit levels below what is recommended by the FDA for blood donation, the visit will be halted immediately. Participants will be asked to stay for 2.5 hours after the study agent has been administered to assess for acute side effects. Two and a half hours was chosen because common withanolides have reached their C_{MAX} by this time based on a previous PK study using Shoden®.⁸⁰ The end-of-visit adverse events questionnaire will be administered by phone and missed safety evaluations (7-hour ECG and vitals, 10-hour CMP, 12-hour vitals) will be collected at the 24-hour visit. After the 24-hour visit, the participant will be withdrawn from the study.

If study staff have difficulties collecting blood samples for any reason, the decision may be made to halt the visit. Participants will be asked to stay for 2.5 hours after the study agent has been administered to assess for acute side effects. If the visit ends before the 7-hour mark, the end-of-visit adverse events questionnaire will be administered by phone and missed safety evaluations (7-hour ECG and vitals, 10-hour CMP, 12-hour vitals) will be collected at the 24-hour visit. Participants will be allowed to remain on the study if difficulties with blood sample collection were the only reason for halting the study visit early.

I.4.2 24- and 48-Hour Visits

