1.6. Four-Week Follow-Up Visit

Participants will be asked to fast for 10-12 hours, excluding water, the night before each four-week follow-up visit in order to collect fasting glucose as part of the CMP. A single blood sample (two teaspoons (10 ml)) and a urine sample will be collected to assess steady state plasma levels and excretion of WS compounds. Returned capsules will be counted to assess for adherence. Participants will have an ECG and blood and urine samples will be sent for safety labs (CBC, CMP, urinalysis, TSH, serum total testosterone, serum DHEA-S). The Geriatric Depression Scale-15 will be administered. At the four-week follow-up visit for the second study period, participants and investigators will be queried as to their perception of the dose sequence administered. This visit is expected to take 45-60 minutes.

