Upon enrollment, each participant will obtain a unique identification number. This number will be associated with all specimens and data collected from that participant. Following the collection of whole blood from the participant, a trained member of the study team will transfer the blood to the specified vacutainer tubes. Blood will be centrifuged in the CTSC's laboratory to separate the plasma for analysis. The isolated plasma will be transferred into labeled tubes and placed on ice until transported by a member of the study team via a sealed Styrofoam cooler labeled with biohazard to the [name] Lab (Richard Jones Hall, OHSU). The plasma and a 50mL aliquot of the urine specimens will be stored in labeled boxes in [name] -80°C freezer.

Electronic data from case report forms and specimen analysis will be entered in REDCap. Analyzed data will be stored in an OHSU approved cloud storage (OneDrive). Only study team members will be granted access to the REDCap database or OneDrive with access specific to their role in the project. Paper records including participant contact information, telephone screening responses, consent forms, electrocardiogram reports, lab results, and paper case report forms will be stored in participant-specific binders, kept in a locked cabinet at the Parkinson's Center of Oregon office suite (Sam Jackson Hall), where [name] is located.

K.3. Sharing of results with participants

All screening laboratory results, performed by the CLIA-certified OHSU Core Laboratory, will be shared with the participant through their medical record. If a screening result is found abnormal

(an incidental finding), the participant will be instructed to share their result with their primary care provider. Electrocardiograms (ECGs) will be performed at the screening visit, PK visits, and four-week follow-up visits. If the ECGs are found to be abnormal, the participant will be instructed to share their result with their primary care provider. As there will be no additional laboratory assessments with clinical implications beyond the screening visit, no results from the study will be shared with the research participant or their provider(s).

K.4. Data, Specimen banking, and Repository Procedures

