- Controlled User Access: REDCap employs a robust multi-level security system that enables researchers to easily implement "minimum necessary" data access for their research staff, including specification of data fields that are identifiers. This feature includes "single click" ability to provide completely deidentified (removing all identified data fields and shifting dates) for analysis or other purposes. User activities are logged to enable auditing of all data access. Access is integrated with OHSU's network such that users who are also OHSU employees are authenticated against their OHSU network credentials.
- Data Integrity: REDCap is jointly managed in accordance with OHSU Information Security Directives by ACC staff and members of OCTRI's Biomedical Informatics Program, ensuring fidelity of database configuration and back-ups. User activities are logged to enable auditing of all data changes.

N. PROVISIONS TO MONITOR THE DATA TO ENSURE THE SAFETY OF SUBJECTS

To ensure participant safety, we will monitor for adverse events (AE) with AE questionnaires, ECGs, and laboratory tests. During the baseline visit and four-week follow-up visit for each study period, participants will undergo an ECG and laboratory testing (CBC, CMP, TSH, testosterone, and urinalysis). At baseline visits, ECG will be repeated 7 hours post-Shoden® administration to assess for cardiac changes and CMP will be repeated 10 hours post-Shoden® administration to evaluate liver and kidney function. Participants whose ECGs and/or lab results reflect abnormalities will be further screened for potential causes of the abnormalities as determined by [name]. We will notify the participant and the participants' primary care physician if blood and urine safety parameters fall outside the normal range or if abnormalities are seen on ECG, and [name] will undertake the necessary steps to ensure appropriate clinical care.

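### K.3 ends by denying that clinically relevant labs follow screening and by barring the sharing of results, which contradicts the scheduled safety labs and Section N's duty to notify

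*Combined protocol and SAP*

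**What the plan says.** **Section K.3 (Sharing of results with participants).** Screening labs go to the participant through the medical record. A participant with an abnormal ECG, including one from a PK or four-week visit, is told to take it to their own provider. The section then ends: "As there will be no additional laboratory assessments with clinical implications beyond the screening visit, no results from the study will be shared". The rest of that sentence names the participant and their provider(s) as the people who will receive nothing.

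**Section N (safety monitoring).** At the baseline and four-week visits of each period, "participants will undergo an ECG and laboratory testing (CBC, CMP, TSH, testosterone, and urinalysis"). Then: "Participants whose ECGs and/or lab results reflect abnormalities will be further screened for potential causes of the abnormalities". The team undertakes to inform the participant and the "primary care physician if blood and urine safety parameters fall outside the normal range or if abnormalities are seen on ECG", and a study clinician is to see that appropriate care follows.

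**Other sections that bear on it.**
- C.2.3, after describing reported liver toxicity and a kidney transplant rejection: "Liver and renal abnormalities will be assessed at the beginning and end of each four-week study period".
- I.4.1: a safety panel at each baseline visit, and a later sample that "will be collected for a repeat CMP at 10 hours post-intervention to evaluate kidney and liver function".
- I.4.1: "If the baseline CBC shows hemoglobin or hematocrit levels below what is recommended by the FDA for blood donation, the visit will be halted immediately". The participant is withdrawn after the 24-hour visit.
- I.6: at four weeks, samples go for "safety labs (CBC, CMP, urinalysis, TSH, serum total testosterone, serum DHEA-S").
- H.3: a clinically significant change in laboratory values after starting the product is a listed reason for discontinuation or withdrawal.

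**The concern.** K.3 is where study staff would look for the rule on disclosing results. Its last sentence gives a reason (no clinically relevant labs after screening) and a rule drawn from it (share nothing). If the reason is untrue, the rule has no basis. If Section N requires the opposite, staff hold two incompatible instructions.

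At stake is an abnormal safety result after dosing, for example a raised liver enzyme on the four-week CMP. Under K.3 read literally, neither the participant nor their physician would hear of it. Under Section N both would. The protocol itself says that safety information in older adults is limited (O.1), and its cited tolerability experience at 480 mg is a single administration in 16 participants (C.2.3, O.1).

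**Working it through.** No statistical figure underlies this point. The check is a count of scheduled labs and a comparison of the two rules.

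**1. Do safety labs follow screening?** Inputs are I.4.1, I.6 and Table 1.

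| Time point, each period | Content | Source |
|---|---|---|
| Baseline visit, pre-dose | CBC, CMP, urinalysis, TSH, total testosterone | I.4.1, Table 1 |
| Baseline visit, 10 hours | CMP | I.4.1, Table 1 footnote |
| Four-week visit | Same panel as pre-dose; I.6 adds DHEA-S | I.6, Table 1 |

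Scheduled time points per completer = 3 per period × 2 periods = **6**.

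Cross-check against the protocol's own blood volume for a baseline visit: one pre-dose and 14 post-dose PK samples at 10 mL, plus 20 mL for safety labs, plus 5 mL for the repeat CMP = 150 + 20 + 5 = 175 mL. This equals the total stated in I.4.1, so the baseline safety labs are part of the planned procedures.

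Six is the scheduled number. If difficult blood draws stop a baseline visit before 7 hours, I.4.1 moves the missed CMP to the 24-hour visit. If the visit stops between 7 and 10 hours, the text does not say that the CMP is rescheduled.

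**2. Do these labs have clinical implications?** The protocol treats them as if they do. A low baseline hemoglobin or hematocrit stops the visit and leads to withdrawal (I.4.1). A clinically significant lab change can end participation (H.3). Abnormal results are investigated for cause and followed by clinical care (N). The premise in K.3 is therefore false.

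**3. Can both rules be followed?**

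| Result after screening | K.3 | Section N | Compatible? |
|---|---|---|---|
| Safety lab in range | Not shared | No duty | Yes |
| Safety lab out of range | Not shared with participant or provider | Both notified | **No** |
| Abnormal ECG | Participant told to pass it on (earlier sentence of K.3) | Both notified by the team | Yes on that sentence, though K.3 omits the team's own notice; not if the closing ban is read to cover ECGs |

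The direct collision is in the second row.

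**4. Does a narrower reading rescue K.3?** One could take the sentence to mean only the withanolide assays. Its words do not allow that: the reason given concerns clinically relevant laboratory assessments in general, and the ban covers results from the study without limit.

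**The case against.** The strongest reply is that the safeguard already exists. Section N is the safety-monitoring section. It is specific, it names whom to notify, and it agrees with H.3 and I.4.1. One stray sentence in K.3 is unlikely to override several consistent provisions, and participants may have been told the right rule in the consent form, which is not available here. Most of this stands, and it sets the weight of the point. It does not remove the contradiction: nothing in the protocol gives N precedence, and K.3 is the section whose title covers this subject.

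Three stronger inferences are tempting, and the documents do not support them.

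- *Abnormal results will be withheld and participants are unprotected.* Section N provides both notification and clinical follow-up. Harm needs staff to follow K.3 instead.
- *The count of lab time points measures the size of the problem.* Section N's duty is conditional on a result being out of range. The documents give no abnormality rate, so the number of actual collisions is unknown, and multiplying the six by the number enrolled would not measure it.
- *Section N already requires the four-week DHEA-S to be reported.* DHEA-S is called a safety lab only in I.6. N's lab list, Table 1 and the Figure 3 legend all omit it. N's general reference to blood and urine safety parameters may cover it, but that is an inference.

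**Conclusion.** The last sentence of K.3 is wrong as written. Its premise is contradicted by six scheduled safety-lab time points per completer with stated clinical consequences, and its conclusion is incompatible with Section N for any out-of-range post-screening safety lab. This is an internal contradiction in an operating rule. It is not a gap in the monitoring design, and it has no bearing on sample size, power, alpha or the PK endpoints.

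It should be corrected because the error sits in the section on sharing results and the remedy is cheap. It does not rank higher because Section N already supplies the protection. The verdict rests on the current text of K.3, N, H.3, I.4.1, I.6 and Table 1, and assumes no rate of abnormal results.

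**What to change.** Delete the last sentence of K.3 and put in its place:

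> Out-of-range post-screening safety laboratory results and abnormal ECGs will be reported by the study team to the participant and their primary care physician as described in Section N. Results of the research withanolide assays will not be shared with the participant or their provider(s).

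This removes the false premise, keeps Section N's condition that only abnormal results trigger notice, and limits non-disclosure to the research assays.

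As a separate clarification, state whether the four-week DHEA-S in I.6 falls under the Section N notification. If it does, add it to N's lab list and to Table 1.

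The cost is one replaced sentence, one clarifying statement and a short IRB modification. There are no new visits, samples, procedures or analyses.

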Safety, tolerability, and pharmacokinetics of an oral *Withania somnifera* product in older adults

NCT06171724

Version Date: 10.10.2024

Title: Safety, tolerability, and pharmacokinetics of an oral *Withania somnifera* product in older adults

Principal Investigator: [name], ND, MS [contact]

Co-Investigators/staff: [name] (Clinical Investigator) [contact]
[name] (Co-Investigator) [contact]
[name] (Study staff)
[name] (Study staff)

A. OBJECTIVES

A.1. Purpose

The purpose of this pilot study is to measure the oral absorption and pharmacokinetics (PK) of compounds from two doses of a standardized *Withania somnifera* extract product (Shoden®) in healthy older adults. Compound levels will be measured in human plasma and urine over 48 hours after acute oral administration and after four weeks' use of Shoden®. Peak exposure and time, total exposure, half-life, and urinary excretion of compounds will be calculated. These data will be used to inform decisions on the dosage and dosing frequency for future phase 1 and phase 2 clinical trials.

A.2. Primary goal

To determine the oral bioavailability and PK of withanolides from two doses of a *Withania somnifera* product (Shoden®) in healthy older adults following single administration and after four weeks' use.

A.3. Endpoints

- Primary endpoints:
 - Peak exposure and time (C_{max} , T_{max}) and total exposure (AUC_{0-t} , $AUC_{0-\infty}$) of withanolides from Shoden® in human plasma after a single administration.
- Secondary endpoints:
 - Half-life ($t_{1/2}$) of withanolides from Shoden® to help determine dosage intervals.
 - Urinary excretion of withanolides from Shoden®
 - Steady-state levels of withanolides after four weeks' use.
 - Tolerability and safety of Shoden® following single administration and after four weeks' use.
 - Feasibility of assessing sleep- and stress-related outcomes remotely using REDCap surveys.

B. SPECIFIC AIMS

Aim 1: Evaluate the oral absorption and PK of selected withanolides from Shoden® in older adults.

- **Hypothesis:** Selected withanolides will be detectable in the plasma and urine at both doses of Shoden®, with significantly greater plasma levels achieved at the 480 mg dose.

Aim 2: Assess the safety and tolerability of Shoden® in older adults.

- **Hypothesis:** A single administration and four weeks' use of Shoden® at 240 and 480 mg per day will be well tolerated and produce no severe adverse events.

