The repository guardian will be [name]. For repository requests, the repository guardian or designee will review the requestor's IRB approval memo, protocol, and repository sharing agreement before samples/data are released. Separate IRB approval/determination will be required for each specific human subject research activity that uses coded data/specimens from the repository. The Guardian or designee will check for genetic opt out status, withdrawn consent for data/samples, and limitations on future use of data/samples. A signed Repository Sharing Agreement will be collected before data or samples are released. The Repository Guardian will ensure that material transfer agreements for the transfer of biological materials and data use agreements for data shared outside of OHSU are executed as applicable. Data and specimen releases will be documented on the repository tracking sheet. Data will be released using OHSU approved cloud storage or secure email. Samples will be hand delivered or mailed in accordance with OHSU dangerous goods shipping policies. Specimens and data will be coded with the participant's unique ID code, visit number, and date of collection. The key for requested specimens and data will be provided separately and with the appropriate IRB approval.

L. DATA ANALYSIS

L.1. Specimen analysis (Aim 1)

Eleven withanolides (withanolide A, withanolide B, withaferin A, withanone, withanoside IV, withanoside V, 12-deoxywithastramonolide, sominone, viscosalactone B, 4-oxo withaferin A, and 2,3-dihydro-3 β -methoxy withaferin-A) have been initially selected based on their availability as reference standards. Final selection of withanolides to be included in the PK analysis will be based on product characterization studies conducted at the Oregon State Mass Spectrometry Center. Only withanolides that are confirmed to be in the test product, or an acid hydrolysate of the test product (mimicking deglycosylation), will be included in the PK analysis.

Targeted analysis of the selected withanolides in plasma and urine samples will be performed using LC-MRM-MS instrumentation at OHSU's BSR/PKCore. The BSR/PKCore has developed

Study Title: Safety, tolerability, and pharmacokinetics of an oral *Withania somnifera* product in older adults

Principal Investigator: [name], ND, MS

IRB#: STUDY00026055

Version Date: 10.10.2024

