a 15-minute LC-MRM-MS method for the BENFRA Center for the analysis of seven withanolides using digoxin-d₃ as an internal standard (section E.3, Figure 2). The BENFRA center (through [name]) is working with the BSR/PKCore lab to include the four additional withanolides in the method and optimize mouse plasma work-up methods for the analysis. These methods will be adapted for human plasma and urine in this study, using commercially available human plasma and urine spiked with reference withanolides under the guidance of [name] and [name], director of the BSR/PKCore.

Each withanolide analyte will be identified by its retention time and characteristic mass spectral fragmentation pattern using selected reactions within a multiple-reaction monitoring paradigm. The peak area ratio to the appropriate internal standard will be identified and evaluated against the standard calibration curve of each analyte prepared by spiking known concentrations into blank plasma. Each analyte's concentration in participant plasma will be used to generate a concentration-time curve for pharmacokinetic profiling. The primary endpoints are the maximum concentration (C_{max}) and its corresponding timepoint (t_{max}) of each withanolide analyte. To determine the rate of elimination (k), linear regression of the plasma concentration against time will be used. This value will be used to determine the elimination half-life ($t_{1/2}$) using the formula $t_{1/2}=0.693/k$. Area under the concentration-time curve from dosing (time 0) to time t (AUC_{0-t}) will be calculated using the linear-log trapezoidal method. Area under the concentration-time curve from dosing (time 0) extrapolated to infinite time ($AUC_{0-\infty}$) will be calculated using the equation $AUC_{0-t} + AUC_{t-\infty}$, where $AUC_{t-\infty} = C_{last}/k_e$. C_{last} is the last observed concentration and k_e is the elimination rate constant. Differences in C_{max} , AUC_{0-t} , $AUC_{0-\infty}$, and $t_{1/2}$ for the two doses of Shoden® will be evaluated using paired t-tests or the non-parametric equivalent Wilcoxon paired test, while differences in t_{max} will be compared between dose groups using chi-square tests of distribution. With numerous analytes of interest, post-hoc multiple comparison adjustments in p-values will be applied using the Holm-Sidak stepwise correction. All final statistical tests will be two-tailed and considered significant at $\alpha=0.05$.

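### The primary endpoints differ between A.3 and L.1 and the Holm-Sidak family is undefined, so the primary status of total exposure and the error rate over the primary comparisons are undetermined

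*Combined protocol and SAP*

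**What the plan says.** A.3 gives as primary endpoints "Peak exposure and time (C_{max} , T_{max}) and total exposure (AUC_{0-t} , $AUC_{0-\infty}$) of withanolides from Shoden® in human plasma after a single administration". Half-life is listed there as secondary.

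L.1 states: "The primary endpoints are the maximum concentration" (Cmax) and the time at which it occurs (tmax), for each analyte. It then explains how half-life and both AUCs are calculated, without calling either AUC primary.

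For the dose comparison, L.1 says that differences in Cmax, AUC0-t, AUC0-inf and half-life "for the two doses of Shoden® will be evaluated using paired t-tests or the non-parametric equivalent Wilcoxon paired test", and that "differences in t_{max} will be compared between dose groups using chi-square tests of distribution". All five parameters are therefore tested, whatever their label.

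On multiplicity, L.1 gives the number of analytes as its reason and says that "post-hoc multiple comparison adjustments in p-values will be applied using the Holm-Sidak stepwise correction", with two-sided significance at 0.05. It does not list the tests in the family. "Eleven withanolides" are selected initially. The final number depends on which are confirmed in the product or its acid hydrolysate.

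L.4 claims 95% power for an effect size of 1.3 (Cohen's d) with 10 completers, from a single paired t-test at 0.05. It illustrates the effect on Cmax of three withanolides only.

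**The concern.** Both sections are current text, and no other section reconciles them. Total exposure is a primary result in one and not in the other. Aim 1 predicts significantly greater plasma levels at the higher dose without saying whether that means peak or total exposure, so it does not settle the matter. If Cmax and AUC point in different directions, a reader cannot tell whether the primary result was met.

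The undefined Holm-Sidak family makes this worse. The correction could run across analytes, across parameters or across both, and the error rate over the primary comparisons depends on which is meant. L.4 allows for none of these, although L.1 commits to adjustment.

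**Working it through.** **Inputs.** Primary parameters: 4 (A.3) or 2 (L.1). Parameters tested between doses: 5 (L.1). Analytes: 11, a provisional maximum (L.1). Two-sided alpha 0.05 (L.1). Ten completers and d = 1.3 (L.4).

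**1. Reproduce the plan's figure.** The power of a two-sided paired t-test comes from the noncentral t distribution with 10 − 1 = 9 degrees of freedom and noncentrality 1.3 × √10 = 4.11. At alpha 0.05 it is 95.4%, which matches the stated 95%. That is one test with no adjustment.

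**2. Count the primary comparisons.** L.1: 2 × 11 = 22. A.3: 4 × 11 = 44. All tested parameters: 5 × 11 = 55.

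**3. First-step level and power.** For a family of m tests, Holm-Sidak compares the smallest p-value with 1 − 0.95^(1/m). Power below is for one paired t-test at that level, with n = 10 and d = 1.3.

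| Tests in family | First-step level | Power |
|---|---|---|
| 1 | 0.05 | 95.4% |
| 11 | 0.00465 | 64.4% |
| 22 | 0.00233 | 51.5% |
| 44 | 0.00117 | 39.1% |
| 55 | 0.00093 | 35.4% |

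**4. Compare the two sections under each possible family.**

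- *Primary parameters × analytes.* The family is 22 tests (L.1) or 44 (A.3). The first-step level is 0.00233 or 0.00117, so adjusted p-values depend on which list is followed.
- *Analytes within each parameter.* Every family has 11 tests, so adjusted p-values are the same under both lists. Each parameter carries 0.05. The error bound over the primary set is 2 × 0.05 = 0.10 (L.1) or 4 × 0.05 = 0.20 (A.3). If the parameters were independent, the figures would be 1 − 0.95² = 0.0975 and 1 − 0.95⁴ = 0.1855.
- *All 55 tests together.* Adjusted p-values are the same under both lists.

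**5. Allow for the later steps.** Holm-Sidak relaxes after each rejection, so the first-step figures are floors when several effects are real. In simulation, with every test treated as a paired t-test at d = 1.3, n = 10 and between-test correlation from 0 to 0.8 (all assumptions), average power per test was about 68–74% for 22 tests and about 52–57% for 44.

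**The case against.** The strongest reply is that the primary label changes nothing that will be computed. The study calls itself a pilot and never describes a confirmatory family. L.1 fixes all five parameters for calculation and dose comparison in advance. It gives the number of analytes as the reason for adjusting, which reads most naturally as correction across analytes within each parameter. On that reading every adjusted p-value is the same under both sections. L.4 also expects differences much larger than d = 1.3.

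Most of this stands, and it rules out three stronger readings that a reader might infer:

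- *That error control simply follows whichever section is used.* The documents do not tie Holm-Sidak to primary status. Only one of the three possible families makes adjusted p-values differ between the lists.
- *That an AUC test could be added or dropped once the data are seen.* The AUC comparisons are planned either way. Only their primary label is open.
- *That true power is 52% or 39%.* Those are first-step floors, conditional on 11 analytes and d = 1.3. They do not describe the chi-square test on tmax, which supplies half of the 22 comparisons.

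The reply does not reconcile the two primary lists or define the family. It also leaves the L.4 power resting on a test with no adjustment.

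**Conclusion.** The contradiction is real and unresolved in the documents. Whether total exposure is a primary result is undetermined, and so is the error rate over the primary comparisons. With 11 analytes the primary set is 22 or 44 comparisons. Under within-parameter correction the error bound is 0.10 or 0.20; only a family built from the primary parameters changes the adjusted p-values.

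The 95% in L.4 is correct arithmetic for one unadjusted test. It overstates first-step power under any of the three families, with 64.4% at best. The sizes rest on 11 analytes and would be milder with fewer. The independence figures ignore the correlation to be expected between Cmax and AUC.

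This should be fixed, but it does not invalidate the design of a pilot in which all the dose comparisons are already specified.

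**What to change.** Before any concentrations are analysed:

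1. Put one identical list of primary endpoints in A.3 and L.1. AUC0-t and AUC0-inf may stay primary, which fits the purpose in A.1 of measuring total exposure; L.1 would then need correcting.
2. State in L.1 whether Holm-Sidak runs across analytes, across parameters or across both, and list the tests in each family.
3. Restate the L.4 power for that family. Say that the paired-t figure does not cover tmax.

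Limiting the primary set to Cmax of the three withanolides in L.4 is possible: first-step power for three tests is 85.3%. It is optional. Those three appear in L.4 because the earlier study of this product measured only them (E.2), and nothing in the plan marks them as primary.

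The cost is wording in A.3, L.1 and L.4. No new data, visits or participants are needed. The stated power becomes less favourable.
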